We plan to conduct a 2-arm parallel-randomized controlled clinical trial (RCT). We aim to include 70 pregnant women between 16-40 years old. Since all interventions will be conducted online, participants will be recruited from any Brazilian state or municipality. Participants will be randomly assigned to either receive intervention via app consisting of behavioral activation (BA) and psychoeducation to promote changes in sleep, nutrition, and physical activity habits, as well as to engage in prenatal care, breastfeeding, and social support, and to stimulate child development, in addition to brief cognitive-behavioral therapy (CBT) (n=35); or to a active control group receiving an educational app with content about gestation, maternal health and mental health, and child development in addition to brief CBT (n=35). Duration of treatment will be eight weeks, during which participants in both groups will be assessed at the beginning (baseline; T0), weeks 3-4 (midpoint; T1), and week 8 (endpoint; T2) in order to evaluate treatment effects. We will also conduct a follow-up postnatal assessment when the child is two months of age (T3).

Inclusion and exclusion criteria

We will include pregnant women with the following characteristics: (a) aged between 16-40 years; (b) having a score of ≥ 7 on the Edinburgh Postnatal Depression Scale (EPDS); (c) gestational age between 17-26 weeks; (d) being literate; (e) owning a functional smartphone with Android for personal use. Participants will be excluded if they meet one of the following conditions: (a) pregnancies classified as being at risk (e.g., hypertension, diabetes, etc), fetal malformation, or congenital disease, (b) visual, auditory or intellectual disabilities, or chronic diseases associated with fetal development alterations, or (c) severe and/or chronic mental illness (e.g., schizophrenia, bipolar disorder).

Procedures

Recruitment and randomization

We will use social media (Facebook, Instagram) advertisements, email, and Whatsapp messages to divulge our study and recruit participants. Women interested in participating in our study will be referred to a website page where they will be provided with written information on the study's aims, procedures, and data collection. Afterwards, participants will

Study protocol and statistical analysis plan

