be required to respond to an online survey containing questions related to eligibility criteria of the study. Eligible participants will be invited to a baseline assessment which will be conducted via internet or telephone. In the baseline assessment, after obtaining informed consent, the participant will be instructed to download the Motherly and register a profile with basic information. Randomization will occur automatically in real time using PHP 7 rand function at the end of registration process [38]. After the first login the participant will already be using one of the two versions of the Motherly app (intervention or active control).

Participants cannot be blinded due to the nature of the intervention. Likewise, blinding of psychologists delivering brief CBT will not be possible. However, all assessments will be conducted by assessors blind to randomization and allocation status.

Assessments and instruments

All assessments will be conducted via the internet (videotelephony) or telephone. Assessment instruments as well as time points at which they will be used are shown in Figure 1. At baseline (T0), we will collect socio demographic information (socioeconomic status, educational level, occupation, income, etc) as well as frequency of use of smartphones, media, and apps. We will also conduct a comprehensive clinical assessment of maternal physical and mental health, perceived stress, personality traits, sleep quality, quality of life, physical activity frequency, and psychological well-being using the following instruments. We describe each instrument that will be used in the assessments below.

The Edinburgh Postnatal Depression Scale (EPDS), a 10-item scale developed to assess pre and post natal depression. It is the most used scale in studies about depression during pregnancy and the postnatal period, largely used in observational studies and clinical trials aiming to measure presence and severity of depressive symptoms. It has been validated for use in Brazil and used in multiple studies throughout the years [12, 39–41].

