Participants allocated to the active control group will have access to a simplified version of the app consisting of educational content about various aspects of pregnancy, maternal physical and mental health, and child development. Active intervention functionalities, such as behavioral activation, activity scheduling, sleep hygiene, among others, will not be present in this simplified version. As with the intervention group, participants from the active control group will receive app notifications to answer questions related to the outcomes of this study. The active control group will also receive four sessions of brief CBT throughout the 8 weeks, with a focus on BA. They will be guided by psychotherapists to plan, schedule, and engage in positively reinforcing activities, and will be aided to develop problem-solving strategies for circumventing barriers to completing scheduled activities. However, implementation of these techniques will be conducted without the aid of the Motherly app (as these functionalities are not present in the active control app). Throughout the four sessions, psychotherapists will monitor participants' adherence, answering questions about the strategies and providing support for solving problems or CBT techniques, such as cognitive restructuring, relaxation techniques, sleep hygiene, stress and anxiety management, among other evidence-based techniques might be used if appropriate to the case. The structure of the sessions will also follow the guide mentioned previously.

Sample Size

We calculated the sample size based on an expected effect size of 0.65 on depressive symptoms, which is based on a previous meta-analysis [115] (difference in means between two independent groups) considering a probability of type I error of 5%, statistical power of 80%, a two-tailed test, and a dropout rate of 15%.

Statistical analyses

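### As described, allocation is a plain rand() draw with no restriction, so 35 per arm is only an expected number and baseline depression is left to chance, while the analysis plan states no baseline adjustment

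*Combined protocol and SAP*

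**What the plan says.** Under Setting and design the protocol says "We aim to include 70 pregnant women between 16-40 years old" and gives both arms the same size: intervention "in addition to brief cognitive-behavioral therapy (CBT) (n=35") and active control "in addition to brief CBT (n=35").

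Under Recruitment and randomization the whole mechanism is: "Randomization will occur automatically in real time using PHP 7 rand function at the end of registration process". No section mentions blocks, strata, minimisation, an allocation list or a limit per arm. Consent, app download, registration and the draw all fall within the baseline session. The woman is using her allocated version from first login. The protocol states that participants and therapists cannot be blinded and that assessors will be.

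Entry requires "having a score of ≥ 7 on the Edinburgh Postnatal Depression Scale (EPDS"), and only women found eligible are invited to baseline. A depression score therefore exists before allocation.

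The primary outcome is the change in prenatal depression from baseline to 8 weeks. Statistical analyses plans multiple imputation and a longitudinal mixed model, and gives no fixed effects and no baseline term.

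**The concern.** A separate random draw for each woman does not secure the stated arm sizes. More importantly, nothing in the design balances baseline depression, and nothing in the analysis plan is said to adjust for it. In a trial of 70, a visible baseline gap on the outcome measure is fairly likely. It would move any contrast that is not baseline-adjusted, and readers would question the result. The screening EPDS could be used for balance with no new data collection. If the T0 EPDS is answered after the woman has seen which app she received, it is also a weaker baseline measure.

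**Working it through.** **Inputs.** From the documents: total 70, 35 per arm, "expected effect size of 0.65 on depressive symptoms", test basis "difference in means between two independent groups", two-sided 5%, power 80%, dropout 15%. Assumed, because the documents give no figure: equal SDs at T0 and T2; roughly normal scores; T0-to-T2 correlation r of 0.3 to 0.7; screening-to-T0 correlation ρ of 0.5 to 1.0. The EPDS is taken as the primary scale. The primary-outcome sentence names none, but the entry criterion and the assessment section point to it.

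**1. The plan's own figure.** n per arm = 2(1.960 + 0.842)² / 0.65² = 37.2, so 38. After dropout, 38 / 0.85 = 44.7, so 45 per arm and 90 in total (92 by t-test). The stated 70 is not reproduced. That is a separate issue, and 70 is taken as given below.

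**2. Arm sizes under simple 1:1 allocation, Binomial(70, 0.5).**
- P(exactly 35:35) = 9.5%
- P(40:30 or worse) = 28.2%
- P(42:28 or worse) = 12.0%
- Mean difference between arms = 6.65 women

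**3. Power cost of unequal arms.** Noncentral t with 68 df and noncentrality 0.65 / √(1/n₁ + 1/n₂), before dropout:
- 35:35: 0.65 / 0.2390 = 2.72, power 76.4%
- 40:30: 0.65 / 0.2415 = 2.69, power 75.6%
- Averaged over the binomial distribution: 75.8%, a loss of 0.6 points

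After 15% dropout the figures are 69.3% and 68.7%, again 0.6 points.

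**4. Baseline gap.** The SE of the standardized difference is √(2/35) = 0.239 SD. P(|gap| ≥ 0.25 SD) = 2[1 − Φ(0.25/0.239)] = 29.6%, or 29.9% averaged over random arm sizes. P(|gap| ≥ 0.5 SD) is about 4%. In 20,000 simulated trials, permuted blocks of 4 and 6 without strata left the chance of a 0.25 SD gap at 29.8%, essentially unchanged.

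**5. What a 0.25 SD gap does without adjustment.** With no treatment effect, a baseline gap g carries through to T2 as rg. A T2 contrast therefore shifts by rg, and a change contrast by rg − g = −(1 − r)g.

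| r (assumed) | T2 contrast | Change contrast | Size as % of 0.65 (T2 / change) |
|---|---|---|---|
| 0.3 | +0.075 | −0.175 | 12% / 27% |
| 0.5 | +0.125 | −0.125 | 19% / 19% |
| 0.7 | +0.175 | −0.075 | 27% / 12% |

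**6. What adjustment does.** Per woman, variance is proportional to 2(1 − r) for a change score and 1 − r² with T0 as covariate. The ratio is (1 + r)/2 = 0.65, 0.75 and 0.85 at r = 0.3, 0.5 and 0.7, so variance falls by 35%, 25% and 15%. The shift in step 5 is removed. A realised 0.25 SD gap then costs a variance factor of only 1 + 0.25²/4 = 1.016.

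**7. What stratification does.** With a median split of screening EPDS, the T0 variance within strata is 1 − (2/π)ρ².

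| ρ (assumed) | SD of gap | P(gap ≥ 0.25 SD) |
|---|---|---|
| none (simple) | 0.239 | 30% |
| 0.5 | 0.219 | 25% |
| 0.8 | 0.184 | 17% |
| 1.0 | 0.144 | 8% |

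Simulation with real blocks, some incomplete, gives 18% at ρ = 0.8 and 9% at ρ = 1.0. Exact 35:35 occurs in 78% of trials with unstratified blocks (difference at most 2) and 55% with two strata (difference at most 6).

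**8. Timing.** The text puts registration and the draw inside the baseline session but does not place the T0 EPDS before them. Only the screening EPDS is clearly measured before allocation.

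**The case against.** Simple randomization is a valid design. Stating 35 per arm beside an aim to include 70 can fairly be read as the expected split. That the draw has no restriction is inferred from silence, because the protocol names the random function and not the code around it. Unequal arms cost almost nothing. A chance gap with an SD of 0.24 is ordinary sampling variation: it averages to zero and is already reflected in the standard error. Automatic real-time allocation with no advance list is also hard to predict, which has value when therapists and participants are unblinded. All of this stands.

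Two further points stand in part. Baseline adjustment makes most of the benefit of stratification redundant, but the plan does not state that adjustment. The change outcome might seem to deal with imbalance already. It does not: it shifts the estimate in the opposite direction, by a similar amount over the assumed range of r.

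A reader might also infer that the allocation sequence cannot be audited, or that women could register twice and be drawn again. The documents are silent on server logs, identifiers and repeat registration, so neither is shown.

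**Conclusion.** The point holds as a gap in specification with a cheap remedy. It is not a flaw that invalidates the trial. As written, 35 per arm is an expectation (9.5% chance of an exact split), baseline depression is left to chance (30% chance of a gap of at least 0.25 SD), and no stated analysis step absorbs such a gap. If one occurs and the model is unadjusted, the estimate moves by 12% to 27% of the planned 0.65. That range rests on r of 0.3 to 0.7, equal SDs and the EPDS as primary scale.

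Three stronger readings are not supported. Unequal arms do not materially damage power: the average loss is 0.6 points. Chance imbalance does not bias the comparison; it costs precision and credibility in the one trial that is run. Nor is the missing block structure the cause of the baseline gap, since blocks alone leave the 30% unchanged. Only stratification (or minimisation) on EPDS reduces that chance, and only adjustment removes its effect on the estimate.

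**What to change.** 1. **Analysis.** Name the EPDS as the primary scale and make T0 EPDS a prespecified covariate in the primary mixed model. This needs one sentence and no new data, and it gives the largest gain: 15% to 35% less variance than an unadjusted change score under the assumed r.

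2. **Allocation.** Replace the plain draw with server-side permuted blocks of random size 4 and 6, stratified by screening EPDS in two levels, and include the stratum in the model. This takes a small change to the server code, a link from the screening score and a protocol sentence. The downside is slightly more predictable allocation, limited by automation and random block sizes. The gain in balance depends on the unknown screening-to-T0 correlation and is modest if that is near 0.5. If simple randomization is kept, say so and label 35 per arm as expected.

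3. **Timing.** Release the allocation only after the T0 EPDS is saved, with one allocation per study ID, so that a repeat registration returns the same arm. The cost is a software check and a fixed order within the baseline session.

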Participants allocated to the active control group will have access to a simplified version of the app consisting of educational content about various aspects of pregnancy, maternal physical and mental health, and child development. Active intervention functionalities, such as behavioral activation, activity scheduling, sleep hygiene, among others, will not be present in this simplified version. As with the intervention group, participants from the active control group will receive app notifications to answer questions related to the outcomes of this study. The active control group will also receive four sessions of brief CBT throughout the 8 weeks, with a focus on BA. They will be guided by psychotherapists to plan, schedule, and engage in positively reinforcing activities, and will be aided to develop problem-solving strategies for circumventing barriers to completing scheduled activities. However, implementation of these techniques will be conducted without the aid of the Motherly app (as these functionalities are not present in the active control app). Throughout the four sessions, psychotherapists will monitor participants' adherence, answering questions about the strategies and providing support for solving problems or CBT techniques, such as cognitive restructuring, relaxation techniques, sleep hygiene, stress and anxiety management, among other evidence-based techniques might be used if appropriate to the case. The structure of the sessions will also follow the guide mentioned previously.

Sample Size

We calculated the sample size based on an expected effect size of 0.65 on depressive symptoms, which is based on a previous meta-analysis [115] (difference in means between two independent groups) considering a probability of type I error of 5%, statistical power of 80%, a two-tailed test, and a dropout rate of 15%.

Statistical analyses

First, continuous variables will be described using central tendency measures and categorical variables will be described using frequencies and cross tabulations. To analyze the potential impact of the intervention on depression symptoms we will use an intention-to-treat (ITT) approach. To perform ITT analyses, we will use multiple imputation by chained equations to include every participant randomized. The effects of intervention on maternal depression (primary outcome) and secondary outcomes will be tested using a generalized linear mixed model for longitudinal data. Estimated marginal means will be extracted from these models to describe primary and secondary outcomes of the study for both groups. Marginal means will be used to plot data. Additionally, we will investigate the potential role of moderators (baseline characteristics, such as socioeconomic aspects and personality traits) of the treatment effect on outcomes using a regression-based approach [116]. Standardized effect sizes will be calculated from the difference between group means using criteria described by Cohen [117]. Tests will be considered significant at $p < 0.05$ and

Study protocol and statistical analysis plan

95% confidence intervals will be reported for all parameters. All analyses will be conducted using STATA 16 and R.

Data safety

All data from the assessments as well as clinical records from CBT sessions will be entered electronically via Research Electronic Data Capture (REDCap) [118], thereby ensuring safety of the data and protections of participants' information.

Staff

All assessments will be conducted by a team of psychologists with expertise in mental health and early childhood development with experience in clinical trials. Assessors will receive training sessions with a focus on presenting study details, as well as in-depth explanations of all instruments used. Brief CBT will be delivered by female psychologists with a certified specialization in CBT and previous experience in treating depression. In order to ensure fidelity and quality of treatment, psychotherapists will receive weekly supervision by a senior doctorate level clinical psychologist ([name]) with clinical background in CBT and BA.

Ethical issues and dissemination

Given that the intervention in this study is non-invasive, the risk for participants can be considered marginal. Participants will be informed that questions in the assessment protocol might cause some level of subjective discomfort, but that they are not obliged to answer them and will still continue in the study. Irrespective of the group to which participants will be allocated, they will benefit from receiving brief CBT by a mental health expert, which can potentially alleviate symptoms of depression or anxiety.

Throughout the study, both intervention and active control groups will be assessed for symptoms of depression, anxiety, sleep, and dietary patterns via app. These data will be available to researchers in real time for monitoring purposes if participants need to be referred to specialized care due to severe symptoms of depression or suicidal ideation. In these cases, participants will be contacted by internet or telephone.

During treatment, participants will be referred to specialized care in case depression symptoms worsen to serious, with suicidal ideation, functional impairment, appearance of psychotic symptoms, among others. Participants presenting mental health issues associated with the COVID-19 pandemic and/or social distancing will be treated with psychological first care techniques adequate to stress-related symptomatology due to adverse conditions [119]. At the end of 8 weeks, participants who do not show remission of symptoms of depression will be referred to specialized mental health services.

This study has been approved by the ethics committee of the University of Sao Paulo Medical School (reference number: 3371750). All participants will be required to provide informed consent. In cases where participants are under age, legal guardians will be required to sign informed consent after participants agree to participate in the study.

Funding

This project is funded by grants from the *Saving Brains* program from *Grand Challenges Canada* and Fundação Maria Cecília Souto Vidigal (grants number SB-POC-1810-20573). None of the project partners involved in the trial has a potential conflict of interest to declare.

References

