The main objective of the study is to test the efficacy of a mental health intervention delivered via smartphone application in addition to brief CBT to reduce depressive symptoms and to promote maternal and child health and well-being in pregnant women with depression. Our primary outcome is the change in maternal prenatal depression from baseline to posttreatment (8 weeks). We will also test the efficacy of the intervention on secondary outcomes assessed during gestation: change in maternal mental health (prenatal anxiety, psychological well-being, perceived stress, depression, depression severity, and sleep quality) from baseline to posttreatment, change in maternal prenatal quality of life from baseline to posttreatment, and change in maternal physical activity levels from baseline to posttreatment. Additionally, we will conduct a postnatal follow-up when the child is 2 months of age to test the impact of the intervention on the following secondary outcomes: change in maternal mental health (postnatal depression symptoms, depression severity, anxiety, psychological well-being, perceived stress, and sleep quality) from baseline to follow-up, change in maternal postnatal quality of life from baseline to follow-up, infant developmental milestones, and social/emotional problems at 2 months of age.

Hypotheses

Participants receiving the Motherly app in addition to brief CBT will show significantly greater reduction in symptoms of depression, as well as greater well-being, better overall mental health, and levels of physical activity compared with participants who receive only educational content in addition to brief CBT. We also predict that children of mothers from the intervention group will show better development in the first two months of age in comparison with children from participants in the active control group.

Methods

Setting and design

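### The stated sample-size inputs require 88 to 92 randomised women, not 70; for the comparison named, 70 gives about 70% power, not 80%

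*Combined protocol and SAP*

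**What the plan says.** The Sample Size section opens: "We calculated the sample size based on an expected effect size of 0.65 on depressive symptoms". It describes the comparison as a "difference in means between two independent groups" and lists the remaining inputs: "considering a probability of type I error of 5%, statistical power of 80%, a two-tailed test, and a dropout rate of 15" per cent. It does not state the resulting number. That appears in the Setting and design section: "We aim to include 70 pregnant women between 16-40 years old", with 35 in each arm.

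Two other sections bear on power. The Objectives and outcomes section defines the endpoint: "Our primary outcome is the change in maternal prenatal depression from baseline to posttreatment (8 weeks"). The Statistical analyses section says that effects "will be tested using a generalized linear mixed model for longitudinal data", with multiple imputation so that every randomised woman is included. Neither section says how the baseline EPDS score enters the model, and no correlation between baseline and week 8 is given anywhere.

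**The concern.** All the inputs to a standard two-sample calculation are given, so the planned number can be checked directly. An effect of 0.65 with a two-tailed 5% test and 80% power needs more than 35 per arm even before any allowance for dropout, yet 35 per arm is said to include a 15% allowance.

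The stake is the only justification given for the size of the trial. A reader of a null result would take it that an effect of 0.65 had a 20% chance of being missed. Under the comparison on which the sample size is said to rest, that chance is about 30%. The problem concerns the planning claim: the false-positive rate is unaffected, and 95% confidence intervals will be reported.

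**Working it through.** **Inputs.** From the Sample Size section: d = 0.65, two independent means, two-tailed α = 0.05, power 0.80, dropout 15%. From Setting and design: 35 per arm, 70 in total.

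**1. Completers needed per arm.**
- Normal approximation: n = 2(z₀.₉₇₅ + z₀.₈₀)²/d² = 2(1.960 + 0.842)²/0.65² = 37.15, so 38.
- Exact (noncentral t): n = 38.14, so 39. Power is 0.7985 at 38 and 0.8089 at 39.

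The requirement is therefore 76 to 78 completers, already above 70 with no dropout.

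**2. Adding 15% dropout.**

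| Completers per arm | × 1.15 | ÷ 0.85 |
|---|---|---|
| 38 (normal) | 43.7 → 44, total 88 | 44.7 → 45, total 90 |
| 39 (exact t) | 44.85 → 45, total 90 | 45.9 → 46, total 92 |

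No two-tailed variant gives 70. The shortfall is 88 − 70 = 18 to 92 − 70 = 22 women.

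**3. What would give 70.** A one-tailed 5% calculation needs 30 per arm (power 0.800), and 30 × 1.15 = 34.5, rounded up to 35 per arm. This is only a possible explanation. The documents do not state it, it contradicts the two-tailed test they do state, and it depends on the multiplication convention: 30 ÷ 0.85 = 35.3 gives 36 per arm, or 72.

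**4. Power with 70 randomised** (two-tailed, noncentral t, equal arms, d = 0.65). 15% dropout leaves 35 × 0.85 = 29.75 per arm.

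| Completers per arm | Power | d detectable with 80% power |
|---|---|---|
| 29.75 | 0.693 | 0.739 |
| 30 | 0.697 | 0.736 |
| 35 (no dropout) | 0.764 | 0.679 |

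Equal arms slightly favour the plan. The Recruitment and randomization section describes a simple random draw with no blocking mentioned ("Randomization will occur automatically in real time using PHP 7 rand function at the end of registration process"). Averaged over the possible splits of 70, power after dropout is 0.687.

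**5. Range under the planned analysis.** This needs a baseline-to-week-8 correlation ρ, which the documents do not give; the values below are assumptions. It also takes 0.65 to be in units of the post-treatment SD, which the documents do not specify. With 29.75 per arm, the effective d is 0.65/√(1 − ρ²) for a baseline-adjusted comparison and 0.65/√(2(1 − ρ)) for a raw change score.

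| Assumed ρ | Baseline-adjusted power | Raw change-score power |
|---|---|---|
| 0.3 | 73% | 55% |
| 0.5 | 81% | 69% |
| 0.6 | 87% | 79% |
| 0.7 | 93% | 89% |

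At 29.75 to 30 per arm, 80% power requires ρ of about 0.47 to 0.48 with baseline adjustment, or about 0.61 for raw change.

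**The case against.** The strongest reply is that the trial will not be analysed by an unadjusted two-group test. A longitudinal mixed model that uses the baseline score could recover the missing power: at an assumed correlation of 0.5, baseline adjustment gives 81% with 70 women. The documents therefore do not show that the trial as analysed has less than 80% power. That much stands, and it is why the 70% figure is tied to the comparison the Sample Size section names.

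It does not rescue the stated calculation. That section claims no gain from baseline, the model is not specified closely enough to know whether there is one, and the gain can be negative: a raw change-score contrast loses power when the correlation is below 0.5. The scale of 0.65 is also open. If it is in change-score SD units, raw change-score power stays at about 69% whatever the correlation, and the 0.61 threshold no longer applies. The correlation thresholds further rest on a two-time-point formula that ignores the midpoint assessment, so they are guides rather than exact requirements.

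A second reply is that multiple imputation keeps all 70 women in the analysis. Imputation does not restore the outcome information lost to dropout, and complete data on all 70 would still give only 76% under the named comparison.

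**Conclusion.** The concern holds. The stated inputs require 88 to 92 randomised women, the range depending only on the formula and the dropout convention, and the plan has 70. For the unadjusted two-tailed comparison on which the calculation is said to rest, with equal arms and 15% dropout, power at 0.65 is 69% to 70%. This conclusion needs no figure from outside the documents. Power under the planned mixed model cannot be derived from the plan; over assumed correlations of 0.3 to 0.7 it runs from 55% to 93%, so the plan cannot claim 80% on that basis either.

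**What to change.** Keep 70 women and replace the power claim in the Sample Size section with a sentence such as:

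> 70 randomised (35 per arm) with 15% dropout gives about 70% power (two-tailed 5%, unadjusted two-group comparison, equal arms) for d = 0.65, and 80% power for d of about 0.74.

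This costs one sentence and no participants; the stated power becomes less favourable.

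If the sponsor prefers to justify 70 by baseline adjustment, three things are needed: a sentence in the Statistical analyses section specifying that the week-8 EPDS comparison is adjusted for baseline EPDS; a stated and sourced correlation (about 0.47 to 0.48 or more, or about 0.61 for a raw change-score contrast with 0.65 in post-score SD units); and a statement of which SD the 0.65 refers to. Randomising 88 to 92 would also make the text consistent, at the cost of 18 to 22 more women; the documents do not say whether that is feasible. Whichever route is chosen, the sponsor should state the formula that produced 70 and confirm whether it was one- or two-tailed.

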At post-intervention (T2), 8-weeks after enrollment, we will conduct a clinical assessment with all instruments used in baseline, with the exception of the SIMP. In addition, we will administer the [55] and the Mobile App Rating Scale (MARS) [56] to assess the overall user experience of the Motherly app (intervention and active control).

Study protocol and statistical analysis plan

At follow-up (T3), infant developmental milestones (motor, cognitive, communication/language) will be assessed when the child is two months-old using the Survey of Wellbeing of Young Children (SWYC). Common pediatric symptoms will also be assessed using the Baby Pediatric Symptom Checklist (BPSC) section of the SWYC. The SWYC was validated in Brazil [57].

All assessments will be conducted by a team of psychologists with expertise in mental health and early childhood development with previous experiences in conducting assessment in clinical trials (NCT02807870, NCT04362098). After assessments at every time point, these professionals will be required to fill questions related to the quality of interview in terms of participant's comprehension, collaboration, and quality of internet or telephone connection. Likewise, psychotherapists will fill questions related to the quality and fidelity of intervention after each session with the participant.

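### Do the two infant outcomes, measured only once, need a model of their own in the analysis plan?

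*Combined protocol and SAP*

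**What the plan says.** The Statistical analyses section gives one model for the whole trial: the primary outcome and the "secondary outcomes will be tested using a generalized linear mixed model for longitudinal data". The only other regression it mentions is for moderators of the treatment effect. It states no distribution, link or random-effects structure. It says that estimated marginal means will describe the primary and secondary outcomes, and that standardized effect sizes will come from differences between group means. It adds that "95% confidence intervals will be reported for all parameters" and "All analyses will be conducted using STATA 16 and R".

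Objectives and outcomes lists the two infant outcomes as "infant developmental milestones, and social/emotional problems at 2 months of age". The maternal outcomes in the same paragraph are worded as change from baseline; these two are not. Assessments and instruments places the milestones at T3 only, using the SWYC, and adds that "Common pediatric symptoms will also be assessed using the Baby Pediatric Symptom Checklist (BPSC) section of the SWYC". Setting and design has a single postnatal visit. The Hypotheses section predicts that "children of mothers from the intervention group will show better development in the first two months of age". Nowhere is an infant score given a cut-off, and no odds ratio or binary infant endpoint is mentioned.

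**The concern.** A longitudinal model needs repeated measurements, and the infants have none: no baseline and no second visit. Read literally, the plan applies to them a model whose time and arm-by-time terms cannot be formed.

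The worry sharpens if a developmental score is dichotomised. A logistic model with a random intercept per child is not identified from one yes/no record per child, and software does not always refuse to fit it. A silent misfit could produce an uninterpretable odds ratio and interval for the only hypothesis the trial states about the child.

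**Working it through.** **1. How much of the trial is involved.** Objectives and outcomes lists 8 prenatal maternal, 7 postnatal maternal and 2 infant secondary outcomes: 8 + 7 + 2 = 17. With 70 women (Setting and design) and 15% dropout (Sample Size), 70 × 0.85 = 59.5, so about 30 infants per arm. The plan gives no figure of its own for the infant comparison.

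**2. Continuous score.** With one record per child the model is y = β0 + β1·arm + u + e, with var(u) = τ² and var(e) = σ². The likelihood depends on the variances only through τ² + σ². The split between them is arbitrary, but β1 is the difference in arm means and its standard error is the usual two-sample one. In a simulated data set with 30 per arm (difference 0.434, SE 0.227), the log-likelihood was −76.3045 whether 0, 25, 50 or 90% of the variance was assigned to u. In R, lme4's linear mixed-model routine refuses this model with an error, which sends the analyst to ordinary linear regression and the same answer.

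**3. Yes/no score.** Now P(y=1 | arm) is the average of expit(β0 + β1·arm + σz) over a standard normal z. Two observed proportions must determine three unknowns (β0, β1, σ). Take 9/30 against 5/30 (assumed counts):

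- Ordinary odds ratio: (9/21)/(5/25) = 2.14.
- Log-likelihood: 9 ln 0.3 + 21 ln 0.7 + 5 ln(1/6) + 25 ln(5/6) = −31.8428.

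| Intercept SD | Odds ratio | Log-likelihood |
|---|---|---|
| 0 | 2.14 | −31.8428 |
| 1 | 2.43 | −31.8428 |
| 2 | 3.26 | −31.8428 |
| 3 | 4.69 | −31.8428 |

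The data cannot choose among these rows. The model with no arm difference also reaches its own maximum equally well at every SD. A likelihood-ratio test of no difference is therefore unaffected; what is undetermined is the scale of the odds ratio.

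**4. What one software default does.** R 4.3.3 with lme4 1.1-37 (logistic random intercept, default Laplace approximation) was run at 30 per arm on all 210 tables with 1 to 20 events per arm, the larger count in arm 1.

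- 12 or fewer events in total: the fit failed in 28 of 36 tables (intercept SD 44.9 to 59.5), 27 of them without a warning.
- 13 to 40 events: it failed in 0 of 174, and the odds ratio equalled the ordinary logistic one.
- Example, 6/30 against 3/30. Ordinary logistic: OR (6/24)/(3/27) = 2.25; SE of log OR √(1/6 + 1/24 + 1/3 + 1/27) = 0.76; 95% CI 0.51 to 9.99; p = 0.29. Default mixed fit: OR 2.37, SE 3.98, 95% CI 0.001 to 5,820, p = 0.83.
- With 10-point quadrature in place of Laplace, the six tables tried gave intercept SD 0 and matched ordinary logistic regression. Stata 16, the other named package, was not run.

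The chance of meeting a failing table depends on an assumed event rate common to both arms: 5% at a rate of 30%, 52% at 20%, and about 91% at 10%. The last figure becomes 99% if tables with a zero-event arm are excluded. Such tables have probability 1 − (1 − 0.9^30)² = 8.3%, they lie outside the 210, and most stopped with an error when run.

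**5. Effect on conclusions.** In 26 of the 27 silent failures both fits are non-significant. The exception is 7 against 1: ordinary logistic p = 0.049, default mixed fit p = 0.70. The silent failures widen intervals and gave no false positive. One table (6 against 1) gave a spurious p near zero, and that one carried a warning.

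**The case for a change.** The strongest case for a change is that the documents never say the infant scores will be continuous. The plan provides for categorical variables in its descriptive analyses, and a generalized model allows a binary outcome. If an analyst did dichotomise, followed the text literally and accepted R's default, the resulting interval could be useless with no warning, although intervals are promised for every parameter. Leaving the model open also leaves a choice to be made once data are in hand, and a sentence would settle it.

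Part of this stands. The form of each infant score is unstated, and the non-identification in step 3 is a mathematical fact. But the harm needs four things together: a split that no section plans, a random intercept kept for unrepeated data, one particular approximation, and few events. The text leans the other way, towards marginal means, mean differences and a hypothesis about degree of development. The risk of choosing a cut-off late concerns how the score is defined, and ordinary logistic regression would share it. Nor is ordinary logistic regression safe with very rare events, since it has no finite estimate when an arm has none. Finally, the tables use 30 per arm, whereas the planned multiple imputation of everyone randomized could put 35 per arm in the fit, so the percentages in step 4 are only indicative.

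**Conclusion.** No change to the plan follows. It names a longitudinal model for two outcomes that are measured once, and any analyst who reaches those outcomes will compare the arms at T3 with ordinary regression. For continuous scores, the reading the text favours, that gives exactly the arm comparison the named model would give, so no result changes.

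The problem is real only for a dichotomised score fitted with a random intercept. That rests on assumptions from outside the documents: the cut-off, the event rates, the random-intercept form and R's default approximation. Even then it touches 2 of 17 secondary outcomes, and in the tables examined it silently altered significance in one. The primary outcome, the 15 maternal secondary outcomes and the sample size are unaffected. How pregnancies without a live-born infant enter the imputation is a separate question, which the choice of model does not raise.
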